### ***Secondary Outcome Analyses***

The secondary outcomes that will be compared between groups will include total time in hypotension, nausea, vomiting, total phenylephrine and ephedrine (mg) doses, total intravenous fluids in labor (mL), changes in fetal heart rate category, presence, or absence of fetal rate decelerations within one hour of initiation of ELA, and hemodynamic variables (CO, CI, SV, SVV). We will report mean  $\pm$  SD for normally distributed continuous data; median (interquartile range) for data not normally distributed or for data with outliers or ordinal data; and number (percentage) for categorical data. Kolmogorov–Smirnov test will be applied to test for normality of data distribution. An unpaired two-tailed t test will be used for comparing parametric data between groups, and Mann–Whitney U and Wilcoxon rank sum tests will be used for nonparametric data. The chi-square test or Fisher exact test will be applied as appropriate for comparing proportions between groups.  $P < 0.05$  will be considered statistically significant.

In Group HPI, we will use mediation and moderation analyses to assess the ELA  $\rightarrow$  Hypotension association explained by hemodynamic parameters: Cardiac Output (CO), Stroke Volume (SV), Stroke Volume Variation (SVV), Systemic Vascular Resistance (SVR).

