## III. Investigational Plan

### 1. **Study design:** Prospective randomized controlled trial

### 2. **Methods:**

a. **Size of study groups(s):** The primary outcomes are 1.) ease and feasibility of use of the ClearSight monitoring system during labor and delivery, post-epidural-labor analgesia placement; and 2.) time-to-treatment of hypotension, defined as MAP <65 mmHg for more than 1 minute. Our initial pilot sample is expected to identify the ability to use the ClearSight monitoring in the labor and delivery suite, the patient adherence to the finger cuff monitors, and the feasibility of hypotension detection at the central monitors. The pilot sample (N = 30) is not expected to demonstrate significant differences in the relation between mode of blood pressure measurement and time-to-treatment of hypotension but should yield an estimate of the potential differences for a continuance of study.

b. **Environment and Estimated timeline to sample size acquisition:** UPMC Magee performs about 7,400 ELA annually, a range of 20-30 ELA daily. Based on a meta-analysis of trials, the estimated incidence of hypotension after initiation of neuraxial analgesia during labor is approximately 19% (range: 3-35%). Our internal data that shows approximately 20-30% of patients receiving ELA require treatment with a vasopressor within the first 4 hours of ELA initiation; we will use the conservative estimate of 20%. Our internal experience with similar trials also informs our timeline: in our prior experiences with similar labor and delivery trials we have achieved a consistent approach-to-recruit ratio of about 25%. Based on our volume, ELA utilization, eligibility criteria, and rates of ELA-associated hypotension, we estimate a total of 5-8 weeks of recruitment. A total of N=30 patients will be enrolled with a predicted 20% (n=6) experiencing hypotension events of interest.

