### c. **Outcomes:**

Primary outcome:

Ease of use of ClearSight blood pressure monitoring system

(0 – 10) Ratings from patient and patients' assigned nurse during ELA

Feasibility of blood pressure monitoring (yes/no response from assigned nurse regarding patient care.

Time-to-treatment of hypotension (minutes)

Secondary outcomes: (only exploratory)

Total time in hypotension with MAP <65 mmHg

Nausea

Vomiting

Total phenylephrine, mg

Total ephedrine, mg

Total intravenous fluids, mL  
Changes in fetal heart rate category  
Presence or absence of fetal heart rate decelerations within 1 hour of initiation of ELA  
CO, CI, SV, SVV

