**e. Protocol specific methods:**

Patients will be screened electronically using the electronic health record upon arrival at the Womancare birth center at UPMC Magee. Patients are eligible if they are pregnant, admitted for labor and delivery, and receiving ELA. If patients are undecided about whether they will receive ELA but are interested in the research, they may be consented and then marked as a "screen failure" if they do not receive ELA. These patients will not be randomized. Patients who receive ELA will be randomized to treatment of hypotension according to conventional monitoring (Group CM) or monitoring by HPI (Group HPI). Randomization will be 1:1 and occurs immediately after informed consent and signature for research activities. Subjects will be informed of their assignment after all research activities and data collection have been completed. Total monitoring time will be 4 hours starting from the initiation of ELA. To enable group comparisons of total time in hypotension, all participants will wear ClearSight and a Conventional Monitoring cuff; Group CM will be blinded to ClearSight output and receive standard care for the treatment of hypotensive events post-epidural-labor analgesia. Group HPI will receive treatment of hypotension according to ClearSight output and specified by the hypotension treatment protocol below.

Clinical research staff who have been trained in ClearSight will apply the device and troubleshoot any problems. Providers will be trained on the monitor, its interpretation, and output, prior to study launch and real time at the time of active study participant enrollment. This training applies only to those participants who will receive non-blinded treatment assignment

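### Vasopressor totals will be mostly zeros, so the planned medians will probably be 0 in both arms and give no usable effect estimate; add the number (%) treated and the number (%) with an event (minor)

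*Combined protocol and SAP*

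**What the plan says.** Section III.2.c (Outcomes) lists the secondary outcomes and labels them exploratory. They include total phenylephrine and total ephedrine in mg, each drug separately, and "Total time in hypotension with MAP <65 mmHg". Under Secondary Outcome Analyses, outcomes that are not normal by a Kolmogorov-Smirnov test are summarised as "median (interquartile range) for data not normally distributed or for data with outliers or ordinal data". For the comparison, Mann-Whitney U and "Wilcoxon rank sum tests will be used for nonparametric data".

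Section III.2.b gives the expected frequency: "approximately 20-30% of patients receiving ELA require treatment with a vasopressor within the first 4 hours of ELA initiation". It plans on the lower end: "A total of N=30 patients will be enrolled with a predicted 20% (n=6) experiencing hypotension events of interest". On allocation, section III.2.e says "Randomization will be 1:1 and occurs immediately after informed consent".

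Neither the proportion of patients given any vasopressor nor the proportion with any hypotensive event appears in the Outcomes list or in the Secondary Outcome Analyses. No method is given for outcomes with many zeros.

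**The concern.** If 20-30% of patients receive a vasopressor, 70-80% have a total dose of exactly zero. The median of such a variable says almost nothing about how often the drug was used. An arm with 10% treated and an arm with 20% treated would normally both report a median of 0 mg. A rank test adds a P value but no estimate of size.

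The simple quantities that would carry the information are how many patients in each arm were treated and how many had an event. Section III.2.b itself plans in terms of the second, yet neither is a stated output. The share treated also bears on a risk that the plan names in its Risks/Benefits section: treatment after a false-positive reading.

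**Working it through.** **Inputs.** Vasopressor rate 20-30% and N=30 (section III.2.b); 1:1 allocation (section III.2.e), so 30/2 = 15 per arm; summary rule and test (Secondary Outcome Analyses).

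**1. The plan's own figure.** 30 × 0.20 = 6 patients with events. This reproduces.

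**2. Does the median rule apply?** Take 15 totals with 2, 3, 4 or 5 patients at 10 mg and the rest at 0 (one equal dose each is an assumption). The Kolmogorov-Smirnov P values are 0.0003, 0.0009, 0.002 and 0.007. Normality is rejected, so the median (IQR) rule is the one that would be used.

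**3. How often are the summaries zero?** Let X be the number treated in an arm, X ~ Binomial(15, p).
- The median is the 8th ordered value, so it is 0 when X ≤ 7. P(X ≤ 7) is 0.9958 at p = 0.20, 0.9827 at 0.25 and 0.9500 at 0.30.
- The upper quartile is 0 when X ≤ 3. P(X ≤ 3) is 0.6482, 0.4613 and 0.2969 at the same rates.

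Multiplying across the two arms:

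| Use in CM / HPI | Both medians 0 | Both upper quartiles 0 |
|---|---|---|
| 20% / 20% | 0.9958² = 99% | 0.6482² = 42% |
| 25% / 25% | 0.9827² = 97% | 0.4613² = 21% |
| 30% / 30% | 0.9500² = 90% | 0.2969² = 9% |
| 20% / 10% (halved) | 0.9958 × 1.0000 = 99.6% | 0.6482 × 0.9444 = 61% |
| 20% / 40% (doubled) | 0.9958 × 0.7869 = 78% | 0.6482 × 0.0905 = 6% |
| 30% / 60% (doubled) | 0.9500 × 0.2131 = 20% | 0.2969 × 0.0019 = 0.06% |

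For Group HPI alone, the chance of a zero median is 79%, 50%, 21% and 5% at true rates of 40%, 50%, 60% and 70%.

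These figures are for any vasopressor. Each drug alone is used by no more patients than that, so its zeros are at least as many. The treatment protocol table names ephedrine but not phenylephrine. If phenylephrine use were 10% (an assumption), both upper quartiles would be 0 in 0.9444² = 89% of pilots.

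**4. Does the planned test still see an effect?** Simulation with 15 per arm, 10 mg per dose and 30% of treated patients getting a second dose (both assumptions):

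| Use in the two arms | Mann-Whitney on mg rejects | Fisher on proportion treated rejects |
|---|---|---|
| 20% v 10% | 10% | 4% |
| 30% v 10% | 27% | 15% |
| 20% v 60% | 58% | 43% |

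The rank test does not do worse than a test of the proportion. Part of its lead is that Fisher's test is conservative here: with 20% in both arms it rejects in 1.6% of simulations, against 4.3% for Mann-Whitney.

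**5. What would the added summaries look like?** Six of 30 with an event has an exact 95% CI of 8% to 39%. With 3 of 15 treated in each arm, the Wilson limits per arm are 7.0% and 45.2%. The Newcombe interval for the difference is then 0 ± √[(0.200 − 0.070)² + (0.452 − 0.200)²] = ±28 percentage points. A trial to detect 20% v 10% with 80% power at two-sided 0.05 would need 199 per arm.

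**The case against.** A reader might infer that the report will show 0 (0-0) in both arms whatever HPI does. The documents do not support that, for three reasons.
- The IQR is part of the planned summary, and at every rate in the plan's range at least one arm is more likely than not to have a non-zero upper quartile.
- The 20-30% is the site's internal experience. Group HPI is also treated on alerts at an index of 75. With the plan's accuracy figures and 20% prevalence, a single assessment would alert in 0.20 × 0.92 + 0.80 × 0.08 = 25% to 0.20 × 0.88 + 0.80 × 0.13 = 28% of patients, and repeated assessments would raise that. Not every alert leads to a vasopressor, because those read as a preload problem receive fluid.
- The list of health-record variables totals vasopressor doses up to delivery, while the rate covers 4 hours, so there may be fewer zeros.

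A reader might also infer that the effect is hidden from the analysis. It is not: the planned test works on ranks.

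Nor does the pilot thereby miss its stated aim. The estimate of potential differences promised in section III.2.a concerns time-to-treatment, which has its own proportional hazards analysis. That model needs to know who was treated, and nausea, vomiting and decelerations are already outcomes reportable as proportions. All this stands. It leaves one gap: treatment in the protocol can be fluid or a vasopressor, so the number of treated patients in that model need not equal the number given a vasopressor.

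Finally, the documents give no figure for the share of patients with zero time below 65 mmHg. Continuous ClearSight recording may find episodes that a cuff cycling every 3 to 15 minutes misses, so the vasopressor rate does not carry over to that outcome.

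**Conclusion.** The point holds as a minor reporting gap. At the plan's own rate the medians of the vasopressor totals will probably be 0 in both arms (90% to 99% of pilots). They would stay so in nearly all pilots if HPI halved use, and in 78% if it doubled use from 20%. The planned summary therefore gives no usable effect estimate for these outcomes. This rests on 15 analysed per arm and on the 4-hour rate applying to the totals. It weakens as Group HPI use rises towards half.

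It does not extend to the rank test, to total fluids if the 500 mL co-load given to every participant is counted, or to the hemodynamic variables. For time below 65 mmHg it is plausible but unquantified. The fix makes the results readable; it does not give N=30 the power to show a difference.

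**What to change.** In section III.2.c and in the Secondary Outcome Analyses:
- Add, by group, the number (%) given any vasopressor and the number (%) given each drug.
- Add, by group, the number (%) with any ClearSight MAP below 65 mmHg lasting more than 1 minute. All participants wear the device, so the measure is the same in both arms.
- Give each proportion as a risk difference with a 95% CI (Newcombe or exact would serve).
- For total dose, report the mean difference with a CI (bootstrap or permutation). Report dose among treated patients as descriptive only, since that subset is defined after randomization.
- State the time window for the dose totals, so that the proportion treated and the total refer to the same period.

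No new data are needed. The cost is a few lines of wording, a little more analysis, and intervals that will be wide at this sample size.

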**d. Patient inclusion, exclusion, and withdrawal criteria:**

Inclusion

Pregnant  
Receiving epidural labor analgesia (ELA)

Exclusion

Non-reassuring fetal tracing at the time of ELA request  
Contraindications to ELA  
Significant cardiac arrhythmias or aortic regurgitation  
Arrhythmia  
Treatment with antihypertensive medications  
Pre-eclampsia with or without severe features  
Preoperative infection  
Inability to use ClearSight device for any reason.  
Incomplete data  
Sustains unintentional dural puncture during ELA placement

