## **ELA Protocol: Combined Spinal Epidural (CSE) Analgesia**

A baseline blood pressure will be recorded immediately prior to the initiation of ELA.

At patient request, an experienced anesthesia provider will perform procedure to place ELA using CSE technique in the sitting position. CSE is chosen due to reliability and rapidity with which hypotension can be predicted within the ELA encounter. A meta-analysis of studies comparing low-dose epidural analgesia with CSE analgesia found no difference in the incidence of hypotension between the two techniques.

The epidural space will be found using loss of resistance to saline. A 25-27g Sprotte needle will be introduced to the subarachnoid space. After confirmation of cerebrospinal fluid (CSF), a spinal dose of 15mcg fentanyl and 2.5mg bupivacaine will be given (this action defines T0 = initiation of CSE). At T0 blood pressure monitoring and data recordings will begin per protocol specified below.

A 19-20g flexible epidural catheter will then be introduced and threaded 5-6cm in the epidural space. Test dose will be delivered through the epidural catheter and will consist of lidocaine 1.5% with epinephrine, 3mL. The anesthesia clinician will declare positive or negative test dose 5 min after administration of test dose. A positive test dose will result in withdrawal from the study.

Maintenance of ELA will be by patient-controlled epidural analgesia using programmed intermittent epidural bolus (PIEB) at our institutional standards: Ropivacaine 0.1% +2mcg/mL fentanyl, 8mL q40min, 8mL demand q8min, maximum hourly volume 24mL. (Smiths CADD®-Solis Infusion System, Infusion Pump, ICU Medical, Dublin, OH). The first PIEB dose is delivered 40 minutes after the initiation of the pump.

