### ***Blood Pressure Monitoring and Hypotension treatment protocol is standardized as below.***

#### **BP MONITORING PROTOCOL**

Group CM	Group HPI
-----------------	------------------

<math>T_0</math> At the time of test dose delivery, automated NIBP cycles will begin q3min for 30 minutes, amounting to a total of at least 10 blood pressure measurements.
 
<math>T_{30}</math> After 30 minutes, NIBP cycles to q15min per existing clinical standards
 
<math>T_{4\text{hours}}</math> Monitoring for research ends
	
<math>T_0</math> At the time of test dose delivery, Clearsight monitoring continues.
 
<math>T_0 - T_{4\text{hours}}</math> ClearSight monitoring is continuous
 
<math>T_{4\text{hours}}</math> Monitoring for research ends

--	--

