### \*\*Hypotension as defined above

**Key:** **MAP:** mean arterial pressure; **CM:** conventional monitoring (standard care); **HPI:** hypotensive prediction index group (ClearSight device and algorithm); **BP:** blood pressure; **SBP:** systolic blood pressure; **NIBP:** non-invasive blood pressure; **IVP:** Intravenous push

e. **Electronic Health Record Variables Collected:**

- Age
- Race/Ethnicity
- Insurance status
- Gravidity
- Parity
- Estimated gestational age
- Body mass index
- Induction vs Spontaneous Labor
- Last known cervical exam at the time of ELA initiation
- Pain score immediately prior to ELA initiation
- Total vasopressor doses from time of ELA initiation until delivery
- Time of hypotensive event start to time of treatment for hypotension
- Changes in fetal heart rate Yes/No
  - If Yes: Time, in minutes, from ELA initiation until category change detected
- Presence or absence of fetal heart rate decelerations within 1 hour of initiation of ELA (yes/no)
- Mode of delivery
- Neonatal weight
- Neonatal Apgar scores
- Neonatal cord blood pH

3. **Risks/Benefits:**

Benefits

Close monitoring and treatment of hypotension

Risks

Loss of confidentiality

Discomfort with devices

Inconvenience answering questions

Risk of obtaining a false positive reading and being given fluids or other management of blood pressure that was not necessary.

4. **Data Analysis:**

a. **Data collection form:** See Appendix

b. **Statistical Analysis Plan**

Descriptive statistics will be calculated for variables and compared between groups. We will report mean  $\pm$  SD for normally distributed continuous data; median (interquartile range) for data not normally distributed or for data with outliers or ordinal data; and number (percentage) for categorical data. Kolmogorov–Smirnov test will be applied to test for normality of data distribution. An unpaired two-tailed t test will be used for comparing parametric data between groups, and Mann–Whitney U and Wilcoxon rank sum tests will be used for nonparametric data. The chi-square test or Fisher exact test will be applied as appropriate for comparing proportions between groups.  $P < 0.05$  will be considered statistically significant.

*Primary Outcome Analysis (Survival Analysis)*

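### The exploratory mediation and moderation analysis takes ELA as its exposure, but every randomized patient receives ELA and no other contrast is named, so no ELA effect can be estimated between patients

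*Combined protocol and SAP*

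**What the plan says.** The last sentence of Secondary Outcome Analyses (III.4.b) reads "In Group HPI, we will use mediation and moderation analyses to assess the ELA" and goes on to make hypotension the outcome, with CO, SV, SVV and SVR as the explanatory parameters. It gives no model, no comparison condition and no time points.

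Other sections that bear on this:

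- **Who is studied.** The inclusion criteria (III.2.d) require ELA. Protocol specific methods (III.2.e) says "Patients who receive ELA will be randomized"; consented patients who do not receive ELA become screen failures and are not randomized.
- **Before ELA.** The Pre-ELA Protocol describes applying the ClearSight device in Group HPI. The ELA Protocol says "A baseline blood pressure will be recorded immediately prior to the initiation of ELA" and has data recordings begin at T0.
- **T0.** The ELA Protocol ties T0 to the spinal dose: "this action defines T0 = initiation of CSE". The BP Monitoring Protocol table sets T0 at the test dose, which comes later, and says of Group HPI: "At the time of test dose delivery, Clearsight monitoring continues".
- **Dose.** All patients get the same spinal dose. Maintenance is partly patient-controlled: "8mL demand q8min, maximum hourly volume 24mL".
- **Status.** Outcomes (III.2.c) labels the secondary outcomes as exploratory.

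**The concern.** Mediation asks how much of an exposure's effect passes through an intermediate variable. Moderation asks whether the exposure's effect differs across levels of another variable. Both need an exposure that takes at least two values in the analyzed data. Here the only named exposure is a condition of entry.

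Software run on the patients as described would drop the ELA term or fail. The analyst might then report the surviving coefficients, which link each parameter to hypotension, under the heading of mediation. A reader would take this as evidence on how ELA causes hypotension, although the data contain no comparison with the absence of ELA. The pilot is meant to lead to a larger study, so the wording could be carried forward.

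**Working it through.** **1. Inputs.** ELA = 1 for every randomized patient (III.2.d, III.2.e). N = 30, allocation 1:1, and a predicted 20% with hypotension (III.2.b, III.2.e). A Group HPI size of 15 is an assumption (30 / 2).

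**2. What a constant exposure leaves.** Let M be one hemodynamic parameter and Y the linear predictor for hypotension.

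- Path from ELA to the parameter: M = a0 + a·ELA. With ELA = 1 this is M = (a0 + a). Only the sum is estimable. Columns [1, ELA]: rank 1 of 2.
- Outcome model: Y = c0 + c'·ELA + b·M = (c0 + c') + b·M. Columns [1, ELA, M]: rank 2 of 3. Only b is separately estimable.
- Indirect effect: a × b. It cannot be computed because a is not estimable. The total effect fails for the same reason as a.
- Moderation: Y = d0 + d1·ELA + d2·M + d3·ELA·M = (d0 + d1) + (d2 + d3)·M. Columns [1, ELA, M, ELA·M]: rank 2 of 4. The interaction d3 cannot be separated from d2.

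**3. Pooling the arms.** Group CM also receives ELA, so with 30 patients [1, ELA] still has rank 1 of 2. What differs between the arms is the monitoring, not ELA. A larger sample does not help either.

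**4. Events available.** The plan's own figure reproduces: 30 × 0.20 = 6. For Group HPI, 15 × 0.20 = 3. Over the plan's cited range of 3% to 35%, the expected number is 15 × 0.03 = 0.45 to 15 × 0.35 = 5.25. At 20%, the chance of 0 or 1 event is 0.8^15 + 15 × 0.2 × 0.8^14 = 0.035 + 0.132 = 0.167, against four candidate parameters.

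The 20% comes from vasopressor treatment within 4 hours, not from MAP below 65 mmHg for more than 1 minute. The Group HPI rate could be lower, because treatment may follow an alert, or higher, because measurement is continuous.

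**5. Whether a before/after contrast would be enough.** It makes ELA vary within patients, but not every model then works. Suppose no patient is hypotensive before ELA and 3 of 15 are afterwards. The odds are 0/15 before and 3/12 after, so the odds ratio has a zero denominator and the logistic ELA coefficient has no finite estimate (separation). A continuous outcome such as MAP avoids this.

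**The case against.** The strongest reply is that a within-patient contrast was intended. ClearSight appears in the Pre-ELA Protocol, and the monitoring table says it continues at the test dose, so some hemodynamic data from before ELA may exist. That possibility stands, and a reader should not infer that none will be available. But monitoring that continues at the test dose need not predate the spinal dose, the ELA Protocol starts recordings at T0, and the analysis sentence does not use a before/after comparison.

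A second reply is that epidural volume can differ through demand boluses. It can, but the analysis sentence does not name dose as the exposure. One might go further and infer that volume is not collected, because the Electronic Health Record Variables list omits it. The documents do not support that: the list also omits nausea, vomiting, intravenous fluids and CO, which are all planned outcomes, so absence from it shows nothing. The appendix forms are not visible.

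A third reply is that the analysis is exploratory and probably meant as a description of mechanism. That lowers the priority. It does not make the ELA terms estimable, and if description is the aim, the text should say so.

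**Conclusion.** The point holds in a limited form. As written, the analysis cannot yield an ELA effect between patients, whether direct, indirect, total or in interaction. What is estimable is the association of CO, SV, SVV and SVR with hypotension among ELA recipients, and about 3 events are expected on the assumptions of 15 patients and 20%.

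The conclusion rests on the visible text: ELA constant by eligibility, and no other exposure named for this analysis. It does not extend to saying that an ELA contrast is impossible in this trial, since the plan could define one. Nor does it touch the primary outcomes or the separate between-group comparison of CO, CI, SV and SVV. This is a low-priority correction that could be made.

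**What to change.** In Secondary Outcome Analyses, replace the mediation and moderation sentence with an exploratory, descriptive analysis:

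- Describe CO, SV, SVV and SVR in Group HPI patients with and without hypotension (ClearSight MAP below 65 mmHg for more than 1 minute), up to first hypotension, first treatment or 4 hours, whichever comes first.
- Report separately the patients treated on an alert before meeting the definition, because their course without treatment is unknown.
- Make no mediation or causal claim.
- Reconcile the two definitions of T0 so that the window start is fixed, and state that the fluid co-load and the change from sitting to lateral position fall around that start.
- Add SVR to the hemodynamic variables in Outcomes and in Secondary Outcome Analyses. Both lists now give only CO, CI, SV and SVV.

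If an ELA effect is still wanted, name the varying exposure (before/after ELA, or timed epidural volume) and confirm that it is recorded. For before/after, use a continuous outcome such as MAP, and say that the change is mixed with the co-load and the change of position.

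**Cost.** The descriptive version is mainly a change of wording, provided SVR is stored with the other ClearSight output. A before/after version needs ClearSight values from before the spinal dose, which may already be available; a dose version needs timed volumes. The downside is that the mediation aim is dropped. Results are descriptive only, not least because stopping the window at first treatment is itself informative.
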